11.1. Sample Size and Power Calculations

The planned sample size is 120 subjects. Since this is the first multicenter study evaluating the effect of ATI-50002 Topical Solution in subjects with stable patchy alopecia areata, the sample size was based upon feasibility issues rather than on a formal power calculation. However, data from 120 subjects (40 per group), utilizing LOCF for missing data, provides 80% power to detect a 24-point difference in percent change from baseline in SALT score between any two treatment groups. This power computation was based upon the assumed standard deviation of 38%. Data from a previous study NCT02197455 showed that the standard deviation in percent change from baseline in the SALT score is 30.3%. The 38% standard deviation assumption used for this power computation was chosen to account for the increase in variance due to the lower baseline SALT entry criteria for this study as compared to NCT02197455.

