11.4. Efficacy Analyses

11.4.1. Primary Efficacy Analyses

The primary efficacy variable will be the percent change from baseline in the SALT score at Week 24 (Visit 10). This represents the percentage of hair regrowth. It will be calculated as the mean of the changes from baseline (Visit 2) SALT score to Week 24 (Visit 10) SALT score, divided by the baseline SALT score and expressed as a percentage. Missing data for the primary endpoint will be imputed using Last Observation Carried Forward (LOCF) methodology. The analysis will be conducted on the relative percent change from baseline over time including all visits using a mixed effect model repeated measures (MMRM). The adjusted mean (LS Mean) for percent change from baseline in the SALT score at each visit, estimated from the MMRM, with the estimated standard error and 95% confidence interval (CI), will be presented in tabular and graphic

format. The difference in the adjusted means between treatment groups and the associated 95% CI of the difference will be provided. No adjustment for multiplicity will be made. The model will include fixed effect terms for treatment, study visit, baseline SALT score group (<50, ≥ 50), and treatment by SALT group interaction. The primary analysis will be based on the Intent-to-Treat (ITT) population. Statistical significance for primary efficacy endpoint will be declared if at least one treatment group comparison at the Week 24 visit has a two-sided p-value less than or equal to 0.05.

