### **3. GENERAL STATISTICAL CONSIDERATIONS**

#### **3.1. SAMPLE SIZE AND POWER**

The planned sample size is 120 subjects. Since this is the first multicenter study evaluating the effect of ATI-50002 Topical Solution in subjects with stable patchy alopecia areata, the sample size was based upon feasibility issues rather than on a formal power calculation. However, data from 120 subjects (40 per group), utilizing LOCF for missing data, provides 80% power to detect a 24-point difference in percent change from baseline in SALT score between any two treatment groups. This power computation was based upon the assumed standard deviation of 38%. Data from a previous study NCT02197455 showed that the standard deviation in percent change from baseline in the SALT score is 30.3%. The 38% standard deviation assumption used for this power computation was chosen to account for the increase in variance due to the lower baseline SALT entry criteria for this study as compared to NCT02197455.

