#### **3.3.3. Multiple Testing and Comparisons**

There are no planned adjustments for multiple comparisons.

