## **5. STATISTICAL METHODS**

Descriptive statistical methods will also be used to summarize the data from this study, with hypothesis testing performed for the primary and key secondary efficacy endpoints. Unless stated otherwise, the term “descriptive statistics” refers to number of subjects, mean, median, standard deviation, minimum, and maximum for continuous data, and frequencies and percentages for categorical data. For categorical variables, the denominator of percentages will be the number of subjects in the treatment group, except for those collected by study visit and/or scheduled time point, in which case the denominator of percentages will be the number of subjects with a non-missing value at the visit and/or the scheduled time point. If a different denominator is used, this will be identified in the summary table.

All data collected during the study will be included in data listings. Unless otherwise noted, the data will be sorted first by treatment group, subject number, and then by date within each subject number. Assessments indicated as ‘Not Done’ will not be included in the listings.

The term ‘treatment group’ refers to ATI-50002 active groups and matching Vehicle group.

All statistical testing will be two-sided and will be performed using a significance (alpha) level of 0.05 unless otherwise stated. P-values will be presented to three decimal places. For the efficacy endpoints, the ATI-50002 treatment groups will be tested versus vehicle via statistical inference.

The statistical analyses will be conducted with the SAS® software package version 9.4 or higher. All analyses will be subject to formal verification procedures. Specifically, results will be independently verified by a second programmer/statistician or independently hand-checked prior to issuance of the draft statistical report. All documents will be reviewed by the lead statistician to ensure accuracy and consistency.

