### **5.2.2. Primary Efficacy Analysis**

Descriptive statistics for the SALT score, change, and percent change from baseline will be presented for each scheduled analysis visit. Percent change from baseline in SALT over time up to Week 24 will be analyzed using a mixed effect for repeated measures (MMRM) model. This primary analysis will utilize the score with imputation for LOCF and will be based on the ITT population. The model will include fixed effect terms for treatment, study visit, baseline SALT score group (<50, >=50), and treatment by SALT group interaction. Within-subject variability will be modeled using a compound symmetry covariance structure. The least squares mean (LS Mean) percent change from baseline in the SALT score at each visit, estimated from the MMRM model, with the estimated standard error and 95% confidence interval (CI), will be presented in tabular and graphic format. The difference in the adjusted means between treatment groups and the associated 95% CI of the difference will be provided.

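### The primary model has a treatment-by-SALT-group interaction but no stated weights for the adjusted means; equal weighting would cost material power from about a 65/35 split of the SALT groups

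*SAP*

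**What the plan says.** SAP 5.2.2 specifies a repeated-measures model for percent change in SALT, fitted to LOCF-imputed ITT data with compound symmetry. On its terms it says: "The model will include fixed effect terms for treatment, study visit, baseline SALT score group (<50, >=50), and treatment by SALT group interaction". Protocol 11.4.1 lists the same terms, ending "and treatment by SALT group interaction". Both then report adjusted means by treatment and their differences. Neither says how those means are averaged over the two SALT groups. SAP section 5 names SAS 9.4 or higher but no procedure or option that would settle it.

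On power, SAP 3.1 says that 120 subjects, 40 per group, "provides 80% power to detect a 24-point difference in percent change from baseline in SALT score between any two treatment groups". It adds: "This power computation was based upon the assumed standard deviation of 38" percent. An earlier study "showed that the standard deviation in percent change from baseline in the SALT score is 30.3" percent, and the larger value allows for the lower SALT entry threshold. Protocol 11.1 makes the same statement. Both say that the sample size rests on feasibility.

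Subjects enter with SALT from 15% to 95%. Randomisation is 1:1:1 by sequential kit number (Protocol 7.2, SAP 3.2), with no stratification by SALT group described. No expected split or cap at 50 is given. SAP 5.2.7 separately repeats the primary analysis within each SALT group.

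**The concern.** Once treatment interacts with SALT group, the model holds two treatment effects, one per group. A single overall effect exists only after weights are chosen. Equal weights give the smaller group as much influence as the larger one although it is estimated less precisely, so the variance of the overall contrast rises as the split moves away from 50/50. The power statement is a plain two-group calculation and does not allow for this.

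Two things are at stake. One is precision of the primary contrast, which can be kept at no data cost. The other is which treatment effect is reported: if the effect differs by severity, equal weights and enrolled-mix weights answer different questions, and the plan does not say which one it asks. The gap spreads further, because SAP 5.2.5 applies the primary method to ALODEX, SALT change and DLQI, and SAP 5.2.3 uses the same interaction structure for episode duration.

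**Working it through.** **Inputs from the documents.** Difference 24 points, SD 38, 40 per arm (SAP 3.1, Protocol 11.1). Testing: "All statistical testing will be two-sided and will be performed using a significance (alpha) level of 0.05 unless otherwise stated" (SAP section 5). Multiplicity: "There are no planned adjustments for multiple comparisons" (SAP 3.3.3), so 0.05 applies to each comparison.

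**Assumptions, because the documents are silent.** Equal weights on the two SALT groups; the same split p/(1-p) in each arm; the same 24-point effect in both groups; 38 as the residual SD within SALT group; a single visit.

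**Step 1: reproduce the stated power.** The standard error of a difference is 38 × √(2/40) = 8.50. Power = Φ(24/8.50 − 1.96) = Φ(0.865) = 80.6%. A two-sample t calculation with 78 df gives 79.7%. Both agree with the stated 80%.

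**Step 2: variance under equal weights.** Each arm's adjusted mean is half of each cell mean, so its variance is (SD²/n) × ¼ × [1/p + 1/(1-p)] = (SD²/n) × 1/[4p(1-p)]. The same factor multiplies the variance of the treatment difference. The effective number per arm is 40 × 4p(1-p).

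**Step 3: power by split** (normal approximation, the method that reproduces the plan's figure).

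| Split | Variance factor | Effective n per arm | Power | Difference detectable at 80% |
|---|---|---|---|---|
| 50/50 | 1.000 | 40.0 | 80.6% | 23.8 |
| 55/45 | 1.010 | 39.6 | 80.2% | 23.9 |
| 60/40 | 1.042 | 38.4 | 79.0% | 24.3 |
| 65/35 | 1.099 | 36.4 | 76.9% | 25.0 |
| 70/30 | 1.190 | 33.6 | 73.5% | 26.0 |
| 80/20 | 1.563 | 25.6 | 61.8% | 29.8 |

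Power stays at or above 80.0% to about 56/44. With t and 114 df, the values at 60/40, 70/30 and 80/20 are 78.4%, 72.8% and 61.1%. If the split also varies by chance between arms, as unstratified randomisation allows, simulated mean power is 79.6% at 50/50, then 77.8%, 71.6% and 58.8% at those same three splits.

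**Step 4: the alternatives.** In a three-arm, two-group design matrix with 40 per arm and the same split in each arm, the variance factor is 1.00 at 50/50, 60/40, 70/30 and 80/20. This holds both for the main-effects model and for observed-share weights with the interaction kept. Power stays at 80.6%.

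**Step 5: sensitivity to the SD.** The factor 1/[4p(1-p)] does not contain the SD. At a residual SD of 34 and a 70/30 split, equal weights give 82.5% against 88.4% for the alternatives. Absolute power is higher, but the variance ratio is still 1.190. With equal weights, 80% is kept at 60/40 if the residual SD is 37.5, at 70/30 if it is 35.1, and at 80/20 if it is 30.7.

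**Step 6: the all-visit model.** The planned model has no treatment-by-visit term, so its treatment contrast averages over six visits. Under compound symmetry with correlation ρ, its variance is (1+5ρ)/6 times the single-visit value. With an assumed ρ of 0.7 the factor is 0.75. A constant 24-point effect then gives 90.3% at 50/50 and 84.8% at 70/30. An effect that builds linearly to 24 averages 24 × 3.5/6 = 14 points and gives 47.7% and 41.4%. Absolute power moves a great deal with these unstated inputs, but the weighting penalty appears in both cases.

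**The case against.** The strongest case against has five parts.

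- **Equal weighting is not in the documents.** This stands. The text is equally compatible with observed-share weights, so the defect is an unstated choice. A reader might infer that the plan prescribes half-and-half weights; it does not.
- **The SD of 38 is not described as a within-group SD.** This stands too. It was raised from 30.3 because of the lower SALT entry threshold, so part of the added variance may be explained by the SALT term. With a total SD of 38 and an assumed 20-point gap between group means, equal weights give 81.7% at 60/40, though 76.0% at 70/30. This changes absolute power, but any lower residual SD helps the alternatives as well.
- **The split may be close to even.** This is possible. The amendment history mentions setting the strata from a blinded look at baseline scores. The current text does not say how 50 was chosen, so neither balance nor marked imbalance can be assumed. The 80/20 row is only the end of an assumed range.
- **The sample size rests on feasibility, and the 80% is illustrative.** This is true and limits the point. A reader might infer that the trial fails to deliver its stated power, or that 73.5% or 61.8% is its real power. The documents do not support that: the figures are for one visit, and the planned all-visit model also depends on correlation and time course, which are not given.
- **Weighting is an estimand choice.** If effects differ by SALT group, power can move in either direction and the two weightings target different quantities. That is a reason to state the choice. The subset analyses drop the SALT term and provide no interaction test, so a supportive test should be kept.

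**Conclusion.** The point holds in conditional form. The primary contrast is not fully defined until weights over the SALT groups are stated. If they are equal, its variance rises by 1/[4p(1-p)]. Under the plan's own 24 points, SD 38 and 40 per arm, and with a common effect at a single visit, the loss against 80.6% is 1.6 points at 60/40, 3.7 at 65/35, 7.1 at 70/30 and 18.8 at 80/20.

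It would be tempting to say that power falls below 80% unless enrolment is exactly even. The arithmetic does not bear that out, since 55/45 still gives 80.2%. The firm part is the relative loss of precision, which does not depend on the SD. The absolute power values rest on the listed assumptions. The change is worth making because it is cheap and, when the effect is common to both groups, the alternatives are at least as precise.

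**What to change.** Before unblinding, amend SAP 5.2.2 so that the primary treatment contrast comes from the model with treatment, visit and SALT group but without their treatment-by-SALT-group interaction. Alternatively, keep the interaction and state that adjusted means are weighted by the observed SALT-group shares of all randomised subjects, pooled over arms. Report the interaction test as supportive. Note in SAP 3.1 that the 80% figure assumes this contrast, and state the same choice for the analyses in SAP 5.2.3 and 5.2.5 that reuse the model.

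The cost is one SAP line or one software option, with no new data. Dropping the interaction departs from Protocol 11.4.1 and should be recorded in SAP section 6; stating the weights leaves the protocol model as it is. The downside is that, if effects differ by SALT group, the estimate describes the enrolled mix and not an equal mix. The group-specific effects remain visible in the SAP 5.2.7 subset analyses.

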### **5.2.5. Secondary Efficacy Analysis**

Descriptive statistics will be presented for all secondary efficacy endpoints.

The mean percent change from baseline in the ALODEX score (percent regrowth); the mean change from baseline in SALT and the mean change from baseline in ALODEX will be analyzed using the methods planned for the primary efficacy analysis. The calculated DLQI total score ranges from 0 to 30. This mean change from baseline in DLQI will also utilize the MMRM analysis as planned for the primary efficacy analysis.

Responder-type analyses are planned based on the SALT, ALODEX, Scalp-ClinRO, and Scalp-PRO. The responder definitions include:

- The proportion of subjects achieving a  $\geq 50\%$  hair regrowth compared with baseline for SALT and for ALODEX scores
- Proportion of subjects achieving an absolute SALT score  $\leq 10$
- Proportion of subjects with  $\geq 2$ -point improvement in Scalp-ClinRO for the Target Area
- Proportion of subjects with  $\geq 2$ -point improvement in Scalp-PRO for the Target Area
- Proportion of subjects with  $\geq 1$ -point improvement in Scalp-ClinRO for the entire scalp
- Proportion of subjects with  $\geq 1$ -point improvement in Scalp-PRO for the entire scalp

The observed proportion of responders and associated 95% CI will be presented. Adjusted rates and 95% CI will be obtained from a logistic regression model with factors for treatment and baseline SALT score group. The p-value for the overall global test that  $\beta = 0$  for each factor will be presented. The adjusted odds ratios (95% CI) for being a responder (active/vehicle) will be presented along with the associated p-value.

The questionnaires Scalp-PRO, Scalp-ClinRO, PhGIS, and SGIS are collected on a 1-5 scale. The frequency of responses for each value will be reported by visit and treatment group. Additionally, change status will be categorized as “Better by x points” when the score decreases from baseline by x points, and as “Worse by x points” when the score increases by x points. For these scales, a stratified Wilcoxon rank sum test will be used at each visit to obtain a p-value to compare the change status of each active treatment group to the vehicle.

For SGITS, PhGIC, and SGIC, the frequency of responses will be summarized for each scheduled collection timepoint. A stratified Wilcoxon rank sum test will be used at each visit to obtain a p-value to compare the results of each active treatment group to the vehicle.

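### The SALT models enter baseline SALT only as below 50 versus 50 and above, although the exact score is available on every subject: a minor, avoidable loss of precision

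*SAP*

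**What the plan says.** SAP 5.2.2 fits the primary MMRM with treatment, visit, and "baseline SALT score group (<50, >=50), and treatment by SALT group interaction". Protocol 11.4.1, with the synopsis, has the same terms: "baseline SALT score group (<50, ≥ 50), and treatment by SALT group interaction". SAP 3.3.1 names the group as the stratum and lists no continuous covariate.

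SAP 5.2.5 sends the mean change in SALT to the primary method, so it inherits the two-group adjustment. The responder endpoints, including at least 50% regrowth on SALT and an absolute SALT score of 10 or less, use a "logistic regression model with factors for treatment and baseline SALT score group".

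No other analysis brings in the numeric score. The exploratory MMRM in SAP 5.2.3 swaps the SALT group for episode duration, and the SALT subset models in SAP 5.2.7 drop the group term.

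The score itself is on hand. Protocol 8.1.1 requires it before randomisation, and it must lie between 15 and 95. Protocol 7.2 and SAP 3.2 describe 1:1:1 allocation by sequential kit number, with no stratification by SALT. The model sections give no reason for preferring the group to the score.

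**The concern.** Under the two-group term, subjects with baseline scores of 15 and 49 are treated as alike, and subjects at 49 and 50 as different. Baseline SALT is the denominator of the primary endpoint and limits how far the absolute score can fall, so it is a natural covariate. With 40 subjects per arm and unstratified allocation, the arms can differ by chance in mean baseline SALT within each group, and the model cannot correct for that part.

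At stake is some precision in the primary and SALT change estimates, and some protection against chance imbalance. The sample size rests on feasibility (SAP 3.1) and subjects who do not complete are not replaced (Protocol 5.8), so precision that costs nothing is worth having.

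**Working it through.** **Inputs from the documents.** Testing: "All statistical testing will be two-sided and will be performed using a significance (alpha) level of 0.05 unless otherwise stated" (SAP 5). Sample: "data from 120 subjects (40 per group), utilizing LOCF for missing data" (SAP 3.1). Target: the design "provides 80% power to detect a 24-point difference in percent change from baseline in SALT score between any two treatment groups". Spread: "This power computation was based upon the assumed standard deviation of 38" percent. Baseline range: 15 to 95.

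**Inputs assumed.** The documents give neither the correlation (rho) between baseline SALT and outcome nor the shape of the baseline distribution. I take rho from 0.1 to 0.5 and four shapes on 15 to 95: uniform, skewed low, skewed high and bell-shaped.

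**1. The plan's own figure.** The standard error (SE) of a difference is 38 × √(2/40) = 8.50. Power is Φ(24/8.50 − 1.96) = 0.806 by the normal approximation, or 0.797 by the noncentral t with 78 df. The stated 80% reproduces, and it takes no credit for baseline adjustment.

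**2. What the cut keeps.** Let k be the squared correlation between the score and its group indicator. For a uniform baseline the group means are 32.5 and 72.5, with shares 35/80 and 45/80.
- Between-group variance: 0.4375 × 0.5625 × 40² = 393.75.
- Total variance: 80²/12 = 533.3.
- k = 393.75/533.3 = 0.738.

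The other shapes give 0.71 (skewed low), 0.66 (bell-shaped) and 0.60 (skewed high).

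**3. Cost of grouping in subjects.** Residual variance is proportional to 1 − k·rho² with the group and 1 − rho² with the score. The ratio minus 1 is the share of sample size given up:

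| rho | uniform | all four shapes |
|---|---|---|
| 0.1 | 0.3% | 0.3 to 0.4% |
| 0.3 | 2.6% | 2.6 to 4.0% |
| 0.5 | 8.7% | 8.7 to 13.4% |

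This compares the score alone with the group alone, without the interaction. It is therefore not the gain from the proposed change, which is in step 5.

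**4. Chance imbalance (uniform baseline).** The SD of the score is √533.3 = 23.1. The SE of the between-arm difference in mean baseline is 23.1 × √(2/40) = 5.2 points. Within groups it is 5.2 × √(1 − 0.738) = 2.6 points, so about half remains. A 1-SE leftover imbalance shifts the treatment difference by rho × 38 × √(1 − 0.738) × √(2/40): 0.4 points at rho 0.1, 1.3 at 0.3 and 2.2 at 0.5. With no baseline term at all, a 1-SE imbalance would shift it by 0.85, 2.55 and 4.25.

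**5. The change proposed.** I added the score while keeping the group and its interaction with treatment. This was simulated with 40 per arm, a uniform baseline, a linear baseline effect, a single Week 24 endpoint and equally weighted LS means. Two separate sets of runs are shown:

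| rho | SE, planned terms | SE, score added | change |
|---|---|---|---|
| 0.1 | 8.59; 8.64 | 8.62; 8.66 | about 0% |
| 0.3 | 8.41; 8.37 | 8.33; 8.30 | about −1% |
| 0.5 | 7.83; 7.83 | 7.56; 7.54 | −3 to −4% |

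At rho 0.5, power in the second set rose from 85.0% to 87.1%.

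**6. Absolute SALT change.** If percent regrowth is unrelated to baseline, with SD 38 and mean 10 to 40%, the implied correlation of baseline with absolute change is about 0.10 to 0.38. A weak link on the percent scale therefore still leaves some on the absolute scale.

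**7. SALT of 10 or less.** Regrowth needed is 1 − 10/baseline: 33% at 15, 80% at 49 and 89% at 95. Most of this gradient lies within the lower group. Even so, with a uniform baseline the two groups explain 59% of its variance, against 80% for a linear term.

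**The case against.** The strongest reply is that little is lost. Baseline SALT is already in the models, and the group captures most of its linear information. The primary endpoint is divided by baseline, which may leave little correlation; at rho 0.1 the change gains nothing. No stated figure fails. All of this stands, and it limits the size of the point. It gives no reason to leave out a score that is already collected.

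Some stronger readings are tempting, but the documents do not support them:

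- **That the cut removes little of the baseline gradient.** It does not: the group keeps about 74% of the linear score under a uniform baseline, and 59% of the variance in the regrowth needed for a SALT score of 10 or less.
- **That the primary result is biased or the power overstated.** Under randomisation the grouping introduces no bias, and the 80% was computed without any baseline adjustment.
- **That SAP 3.1 shows baseline SALT predicts the mean outcome.** The SD of 38, against 30.3 in the previous study, "was chosen to account for the increase in variance due to the lower baseline SALT entry criteria for this study". That concerns variance, and a linear covariate does not deal with unequal variance.
- **That all SALT intervals would narrow.** This fails for the logistic models, where adding a prognostic covariate generally widens the odds-ratio interval and changes the conditional odds ratio. In a simulation of the SALT endpoint of 10 or less (40 per arm, uniform baseline, mean regrowth 10 versus 34, SD 38, unrelated to baseline), the median SE of the log odds ratio rose from 0.88 to 0.91. Power rose only from 12.7% to 14.3%.

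**Conclusion.** The point holds as a minor efficiency weakness. Every SALT model uses the baseline score in two groups when the exact value is available on all subjects and allocation is not stratified by it. For the primary MMRM, adding the score to the planned terms would change the SE by between nothing and about 4% for correlations of 0.1 to 0.5. It would also allow adjustment for the half of a chance imbalance that the group misses, worth 0.4 to 2.2 points of treatment difference per 1 SE, against a 24-point target.

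These sizes rest on an assumed correlation and baseline shape, a linear baseline effect and a single-endpoint simplification of the repeated-measures model. A non-linear relation would change them. That the score is collected but unused rests on the documents alone.

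**What to change.** In SAP 5.2.2 and Protocol 11.4.1, with the synopsis, add baseline SALT as a continuous covariate centred at the overall mean. Keep the SALT group for the planned interaction and subset analyses. Add the score likewise to the SALT change model in SAP 5.2.5, and align SAP 3.3.1. Because SAP 5.2.5 and 5.2.7 define other analyses by reference to the primary one, the wording should say which of them carry the score.

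For the SALT-based logistic models, the score may be added to account for the gradient within groups. Expect at most a small gain in power, and make no claim of narrower odds-ratio intervals.

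The cost is one term and one degree of freedom per model, plus matching text, with no new data. Make the change before unblinding, since adding a covariate afterwards would look data-driven.

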### **5.2.3. Additional Analyses of the Primary Endpoint**

The statistical methods for the main analysis will be repeated using the PP population. The analysis will also be performed using the observed data without imputation for missing in both the ITT population and the PP population.

Another exploratory MMRM analysis for the primary endpoint will be performed with factors for the duration of current episode of patchy alopecia (< 2 years, >= 2 years) and the treatment by duration of episode interaction replacing the baseline SALT score group and treatment by SALT group interaction factors. This analysis will be performed in both the ITT population and the PP population using data with LOCF imputation.

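### Compound symmetry in SAP 5.2.2, in a model with no treatment-by-visit term, cannot support the promised Week 24 inference; the two must be changed together

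*SAP*

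**What the plan says.** On covariance, SAP 5.2.2 is explicit: "Within-subject variability will be modeled using a compound symmetry covariance structure". It names no alternative structure, robust standard error, degrees-of-freedom method or fallback. The protocol names no structure.

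On fixed effects, SAP 5.2.2 reads: "The model will include fixed effect terms for treatment, study visit, baseline SALT score group (<50, >=50), and treatment by SALT group interaction". Protocol 11.4.1 and the protocol synopsis give the same terms. No list includes treatment-by-visit.

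On what is to be reported, SAP 5.2.2 promises "The least squares mean (LS Mean) percent change from baseline in the SALT score at each visit, estimated from the MMRM model", with standard errors and 95% intervals. Under the success rule in Protocol 11.4.1, significance is declared if "at least one treatment group comparison at the Week 24 visit has a two-sided p-value less than or equal to 0.05".

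The primary analysis uses LOCF, so each subject has a value at each of six post-baseline SALT visits (Weeks 4, 8, 12, 16, 20 and 24). SAP 5.2.5 says that percent change in ALODEX and change in SALT and ALODEX "will be analyzed using the methods planned for the primary efficacy analysis", and it extends the same model to DLQI. SAP 5.2.3 repeats the model without LOCF: "The analysis will also be performed using the observed data without imputation for missing".

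**The concern.** Compound symmetry imposes one variance and one correlation on all six visits. Percent change from baseline is zero for everyone at the start, and subjects are enrolled with no current spontaneous regrowth. Spread that widens as some regrow and others do not is therefore a natural expectation, as is stronger correlation between neighbouring visits than between distant ones. Under that pattern compound symmetry replaces the Week 24 variance with an average that includes quieter early visits, and any quantity specific to Week 24 gets too small a standard error.

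The fixed effects add a second problem. Without treatment-by-visit, the model holds a single treatment difference for all visits, so it contains no separate Week 24 comparison for the success rule to use. At stake are the meaning of the primary estimate, the width of the Week 24 intervals, and the error rate of the Week 24 test if someone repairs only half of the model.

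**Working it through.** **Inputs.** From SAP 3.1 and 5.2.2 and Protocol 11.1 and 11.4.1: 40 per arm, three arms, SD 38, difference 24, two-sided 5%, six visits, LOCF. Assumed, because neither document gives them: SD rising linearly from r × 38 at Week 4 to 38 at Week 24, with r = 1, 0.7, 0.5, 0.33 or 0.17; AR(1) correlation ρ between visits; SALT strata split equally.

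**1. The plan's own figure.** SE of a Week 24 difference = 38 × √(2/40) = 8.50. Power = Φ(24/8.50 − 1.96) = 80.6%, which agrees with the stated 80%. The matching 95% half-width is 1.96 × 8.50 = 16.7 points.

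**2. The model as listed.** With complete data and no treatment-by-visit term, the treatment difference is the difference in subject means over the six visits.
- *Error rate.* In null simulations (10,000 trials per scenario, ρ = 0.6 and 0.9) type I error per comparison was 4.7% to 5.3% for every r. With 20% drop-out filled by LOCF (r = 0.5 and 0.17, ρ = 0.8) it was 4.6% to 5.2%. Model and empirical SE agree, for example 5.80 against 5.81 at r = 0.5, ρ = 0.9.
- *What is estimated.* For a benefit rising linearly to 24 points, the visit differences are 4, 8, 12, 16, 20 and 24. Their mean is 84/6 = 14.0.

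**3. Per-arm Week 24 LS means in the model as listed.** Approximate coverage = 2Φ(1.96 × model SE / empirical SE) − 1.

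| r | ρ | Model SE | Empirical SE | Coverage |
|---|---|---|---|---|
| 0.7 | 0.6 | 4.12 | 4.47 | 93% |
| 0.5 | 0.6 | 3.69 | 4.31 | 91% |
| 0.17 | 0.6 | 3.06 | 4.06 | 86% |
| 0.7 | 0.9 | 4.82 | 5.16 | 93% |
| 0.5 | 0.9 | 4.28 | 4.79 | 92% |
| 0.17 | 0.9 | 3.47 | 4.34 | 88% |

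**4. Treatment-by-visit added, compound symmetry kept.** With balanced data the fitted variance is the mean of the visit variances. So k = √(mean visit variance / Week 24 variance), type I error = 2(1 − Φ(1.96k)), and the printed half-width = 16.7k. For r = 0.5: (0.25 + 0.36 + 0.49 + 0.64 + 0.81 + 1)/6 = 0.592, so k = 0.769.

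| r | k | Type I error | Simulated | Half-width (correct: 16.7) |
|---|---|---|---|---|
| 1 | 1.000 | 5.0% | 4.8–4.9% | 16.7 |
| 0.7 | 0.856 | 9.3% | 9.2–9.4% | 14.3 |
| 0.5 | 0.769 | 13.2% | 12.8–13.0% | 12.8 |
| 0.33 | 0.704 | 16.7% | 16.4–16.7% | 11.7 |
| 0.17 | 0.649 | 20.3% | 20.2–20.4% | 10.8 |

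With 20% LOCF drop-out at ρ = 0.8 the rates were 12.3% (r = 0.5) and 19.5% (r = 0.17).

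**5. Unstructured covariance adopted, treatment-by-visit still absent.** The common difference is then weighted by w = Σ⁻¹1 / (1′Σ⁻¹1), which favours the low-variance early visits. Taking the true Σ and the linear rise to 24 points, the estimate at ρ = 0.85 is 8.3 (r = 0.7), 4.5 (r = 0.5) and 2.0 (r = 0.17). At ρ = 0.6 and r = 0.7 it is about 11. Compound symmetry gave 14.0.

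**The case against.** A reader who sees a Week 24 success rule beside an equal-variance structure might infer that the primary test, as planned, runs at 9% to 20%. The documents do not support that. The fixed effects are listed in full and omit treatment-by-visit, and LOCF completes the data. The test is then a comparison of subject means between arms, and it is valid whatever the within-subject covariance. Its error is about 5%, and the interval for the treatment difference is correct for the average it estimates. The 9% to 20% range belongs to a model that the plan does not list. This part of the objection stands.

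It is also fair that the growth in variance is assumed. The documents give a single SD of 38 and no between-visit correlation. Under constant variance the harm in steps 3 and 4 disappears. The protocol's silence on covariance is not a conflict either, since supplying such detail is the SAP's job.

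The objection does not rescue the Week 24 inference. Read literally, the plan has no Week 24 comparison. Read so as to produce one, it needs the interaction, and compound symmetry then becomes harmful if variance grows. The per-arm Week 24 intervals, which are tabulated and plotted, are exposed even under the literal reading.

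**Conclusion.** The concern holds in this form: the covariance and the fixed effects together cannot deliver the Week 24 inference that the plan promises.

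- *Regardless of variance pattern:* the model as listed reports the Weeks 4 to 24 average difference, here 14 points for a linear rise to 24.
- *If variance grows (r from 0.7 to 0.17):* per-arm Week 24 intervals cover about 93% down to 86%. Adding the interaction while keeping compound symmetry takes the Week 24 test to about 9% to 20%.
- *If variance is constant:* coverage and test size are nominal, and only the averaging problem remains.

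The sizes rest on linear SD growth and AR(1) correlation, and step 3 also on the equal strata.

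Two limits apply. The six-visit figures do not transfer to DLQI, which has three post-baseline visits (Weeks 4, 12 and 24). In the observed-data runs the balance that protects the between-arm test is lost, and likelihood-based handling of drop-out depends on a suitable covariance; that effect was not quantified. The familywise error of about 9% from two unadjusted comparisons under an at-least-one rule is a separate multiplicity matter.

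**What to change.** In SAP 5.2.2, and in the matching model text of Protocol 11.4.1 and the synopsis, make two changes in one edit:

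1. Add treatment-by-visit to the fixed effects, and name the Week 24 contrast of each active arm with vehicle as the primary comparison.
2. Replace compound symmetry with an unstructured covariance and Kenward-Roger degrees of freedom. Pre-specify the fallback if the model does not converge: heterogeneous Toeplitz, then heterogeneous AR(1). Do not fall back to an equal-variance structure.

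Neither change should be made alone. The first alone exposes the test to the inflation in step 4; the second alone moves the estimate further from Week 24, as in step 5.

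Carry both changes to the ALODEX, SALT change and DLQI models and to the observed-data runs. The baseline-SALT and whole-scalp subset models in SAP 5.2.7 reuse this model on fewer subjects, so the fallback matters most there.

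The cost is a few sentences and model options. Covariance parameters rise from 2 to 6 × 7/2 = 21, which 120 subjects with six visits can support. The Week 24 half-width becomes about 16.7 points at SD 38, wider than compound symmetry would print under growing variance, but consistent with the plan's own power calculation.
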